7.3 Duration of Participation

The patients will be contacted on post –procedure Day 1, 2 and 7. During the phone call, they would be asked about their original complaints (headache, neck spasm), and if they have any new symptoms or discomforts.

The participants will be contacted by phone about 1 month after the procedure to ask if they have any residual neck or back pain or any other side effect. They will also be asked if they are satisfied with their management of PDPH

The follow-up phone calls will be made even if the SPG block fails and the subject opts for either an epidural blood patch or conservative management.

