1.3 Secondary Study Endpoints

1. To monitor any complications due to SP ganglion block
2. To measure patient satisfaction
3. To monitor any residual effects at 1 months after the SP block

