2.0 Background

2.1 Scientific Background and Gaps

Lumbar puncture is a commonly performed diagnostic procedure in medicine and also for anesthesia. Inadvertent dural puncture can occur during epidural anesthesia and placement of an epidural catheter. Headache after a dural puncture is not uncommon and is excruciatingly painful. Most often it is self-limited and the pain subsides within 1-2 weeks. However, if left untreated, it can lead to considerable morbidity including chronic neck and back pain, subdural hematoma, seizures and even death.

According to the Headache Classification Committee of the International Headache Society, headache after lumbar puncture is defined as “bilateral headaches that develop within 7 days after a lumbar puncture and disappears within 14 days. The headache worsens within 15 min of resuming the upright position, disappears or improves within 30 min of resuming the recumbent position”. This definition helps to avoid confusion with migraine or simple headache after lumbar puncture.

Currently, the standard practice to manage this headache is to do an epidural ‘blood-patch’, wherein an anesthesiologist performs an epidural puncture in the lumbar spine after numbing the skin and subcutaneous tissue with 2-3 ml of 2% lidocaine and injects 20-30ml of the patient’s blood into the epidural space. The intention is for the blood to clot and seal the dural puncture. This is effective about 90% of the time and can be repeated if it fails. Introduction of infection, arachnoiditis, or another inadvertent dural puncture are possible complications. Some patients opt not to have the epidural blood patch for fear of another inadvertent dural puncture and choose the conservative management.

The other forms of therapy are strict bed rest for up to 7 days, hydration, caffeine, and epidural saline infusion. There are case reports of managing PDPH with administration of ACTH. There are a few case reports about use of SP ganglion block for PDPH but no prospective studies looking at onset, duration, side effects and long term follow up after Sphenopalatine ganglion block.

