7.2 Study Procedures

7.2.1 Study Intervention:

A urine pregnancy test will be done for all non-post-partum women.

Once the patient consents to participate in the study the following will be done.

- The worst pain score (on a scale 0-10) that the patient experiences while sitting at the edge of the bed for 5 minutes, will be recorded.
- An IV catheter will be placed and an infusion of IV fluid will be started, if the patient does not have already.
- Continuous ECG, pulse-oximeter and non-invasive blood pressure monitoring will be established and a skin temperature will be recorded.
- The patient will be placed in the supine position with the neck slightly extended.

Sphenopalatine block

Anatomy: The Sphenopalatine or the Pterygopalatine ganglion is a small (5 mm), parasympathetic ganglion located in the pterygopalatine fossa, posterior to the middle nasal turbinate. It is separated by a thin layer of connective tissue and mucosa from the nasal cavity.

Lidocaine (2%) Swab Preparation:

Use of cotton-tipped plastic applicator with 2% Lidocaine jelly applied (see section 7.4.6.3): One 2% lidocaine treated cotton-tipped applicator will be gently inserted into each nostril, along the floor of the nose. Slight rotatory motion of the applicator will be used to insert it as far as it goes with the intention to reach the nasopharyngeal wall (posterior wall of the nose). At that position the applicator will be left undisturbed for 5 minutes. The swabs will be taken out and this will be repeated twice more, using fresh 2% lidocaine treated swabs. The whole procedure will take about 30 minutes.

After the procedure the patient will be asked for any side effects and if they are comfortable will be asked to sit up with their legs dangling over the side of the bed. If they can sit for about 15

minutes without pain and are hemodynamically stable, they will be asked to stand and walk. At any stage the headache returns or they cannot sit up or stand for any other reason, they will be made to lie down.

If the headache resolves, they will be discharged to go home, if acceptable by the primary physician. The patient will be encouraged to drink plenty of fluids and caffeinated drinks and get as much bed rest as possible for the next 3 days.

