After the patient has given informed consent, 2% Lidocaine jelly (Glydo) obtained from pharmacy supply, just like any other standard of care medication and will be administrated and documented as any other standard of care medication. Post research intervention, a study team member will securely email [name], Senior Representative Patient Accounts, at [contact] within 24-48 hours with identifiers (MRN, FIN, and Date of Service). She will manually pull the charge from the patient's bill and direct the research charge to the Sponsor, in this case the Department of Anesthesiology and Perioperative Medicine.

On Day 1, 2, and 7 after the procedure, one of the investigators will call them to ask a set of questions about the headache and any side effects. A follow up phone call, at 1 month after the SP ganglion block, will be made to ask for any residual headache or other symptoms and their satisfaction with the management. (Data Sheet)

If the headache does not get relieved, the patient will have the option to undergo an epidural blood patch or opt for a conservative management of bed rest, analgesics and oral fluids. These options will also be available if the headache were to recur after the patient goes home.

We will also collect information (demographic details, past medical history, details of the procedure that led to the current headache) from the patient's medical record for this research.

7.2.2 Post-treatment Days 1, 2, 7

Patients will be followed up by either a visit, if the patient is an in-patient, or by phone if the patient is at home.

Questionnaire – pain relief, residual pain (intensity and location), side effects, nasal bleeding (See Data Sheet in supporting materials)

7.2.3 1 month Post-treatment

A follow up phone call at 1 month after the SP block will be made to ask for any residual headache or other symptoms and their satisfaction with the management.

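### No pre-block record of neck or back pain is specified, so at 1 month existing pain may not be reliably separable from new pain, above all back pain

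*Combined protocol and SAP*

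**What the plan says.** Secondary endpoint 3 (section 1.3) reads "To monitor any residual effects at 1 months after the SP block". It does not say what residual is measured against.

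The 1-month call is described in two ways:
- Sections 7.2.1 and 7.2.3 say the call is "to ask for any residual headache or other symptoms and their satisfaction with the management".
- Section 7.3 says it is "to ask if they have any residual neck or back pain or any other side effect", plus satisfaction. It does not name headache.

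Before the block, section 7.2.1 lists one symptom item: "The worst pain score (on a scale 0-10) that the patient experiences while sitting at the edge of the bed for 5 minutes". From the medical record the study takes "demographic details, past medical history, details of the procedure that led to the current headache".

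At Days 1, 2 and 7, section 7.2.2 collects pain relief, the intensity and location of any remaining pain, side effects and nasal bleeding. It refers to a Data Sheet that is not among the documents. For the same contacts, section 7.3 asks about the complaints the subject came with, giving headache and neck spasm, and separately about anything new.

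The design is open-label and single-arm with thirty subjects (7.1, 8.1). Section 8.3 plans descriptive statistics, including the frequency of side effects at one week and 1 month.

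**The concern.** With no control group, the subject's own state before the block is the only reference for a symptom reported at 1 month. Neck and back pain are foreseeable in these patients for reasons unrelated to the block. Inclusion criterion 3 requires a lumbar puncture, or an accidental dural puncture during epidural placement, within the previous 7 days. Section 2.1 says the untreated condition can lead to "considerable morbidity including chronic neck and back pain, subdural hematoma, seizures and even death".

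Section 7.3 groups neck and back pain with other side effects, and section 8.3 counts side effects at 1 month. Pain that came with the original puncture, or preceded it, could therefore enter the side-effect table for the block. In the other direction, pain that has improved since entry would look the same as pain that is new. Section 8.2 intends the data to support planning of a larger study, so a blurred side-effect profile could be carried forward.

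**Working it through.** The plan gives no figure on this point. The check sets what is recorded at each time beside what is asked at 1 month.

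| Time | Neck pain | Back pain |
|---|---|---|
| Before the block (7.2.1) | Not listed; pain score has no location | Not listed; pain score has no location |
| Medical record (7.2.1) | Only if in past history or procedure details | Only if in past history or procedure details |
| Days 1, 2, 7 (7.2.2, 7.3) | Neck spasm named as a presenting complaint; location of remaining pain recorded | Not named; could appear under location or as a new symptom |
| 1 month (7.2.1, 7.2.3) | Not named; other symptoms | Not named; other symptoms |
| 1 month (7.3) | Named | Named |

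Take a subject who reports back pain at 1 month.

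1. If no back pain was recorded at Days 1, 2 or 7, the pain can be recognised as late in onset. The listed data are enough, provided the location field was completed for all pain and not only for headache.
2. If back pain was recorded at Day 1, it may have been present before the block or may have begun after it. No listed pre-block item decides between the two. Past history may show a long-standing problem, but need not show pain that began with a puncture a few days earlier.
3. Whether the pain is worse, unchanged or better than before the block cannot be stated in either case. No pre-block severity is listed for that site, and neither description of the 1-month call lists a severity item.

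Neck pain differs in one respect. Because 7.3 treats neck spasm as a presenting complaint, the caller is presumably expected to know whether it was there at entry. No listed pre-block step records it.

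A further source of back pain arises during follow-up. Sections 7.2.1 and 7.3 allow an epidural blood patch when the block fails, and these subjects are still called. Section 2.1 describes the patch as an epidural puncture in the lumbar spine. It does not list back pain among the complications, but a second lumbar needle procedure is a plausible cause.

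The documents give no frequency of neck or back pain, so the number of subjects affected cannot be calculated. The sensitivity of the result can: with all thirty reached at 1 month, each subject wrongly counted moves the reported frequency by 1/30 = 3.3 percentage points.

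**The case against.** The strongest reply is that the protocol does separate old from new. At Days 1, 2 and 7 it asks about presenting complaints and new symptoms as two questions, and it records where any remaining pain is. Past history is abstracted as well. This stands against any claim that the endpoint can never tell new symptoms from old. It does not supply a pre-block record of back pain, and Day 1 is already after the block.

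Second, the Data Sheet was not supplied and may contain a baseline item. A reader might infer that the study collects no such baseline at all. The documents do not support that; they show only that the protocol text specifies none.

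Third, the endpoint speaks of effects after the block, not effects caused by it. Persisting pain from the puncture may be part of what it is meant to describe. That is a fair reading of section 1.3. The difficulty comes from 7.3, which groups the pain with side effects, and from 8.3, which counts side effects. Recording the pre-block state serves either reading.

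Fourth, a reader might infer from 7.3 that headache would not be asked about at 1 month. That is weak. This is a single-centre study, the investigators make the calls, and 7.2.1 and 7.2.3 both name headache. Both descriptions are open-ended. The wording should be aligned, but the data are unlikely to be lost.

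Finally, a baseline would not settle attribution in subjects who go on to a blood patch. That is correct and calls for showing those subjects separately.

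**Conclusion.** The concern holds in a limited form. The protocol text lists no pre-block assessment of neck or back pain, asks about both at 1 month as residual, and places them with side effects whose frequency is to be reported. Pain present at entry may therefore not be reliably separable from new pain. The gap is widest for back pain, which is named neither at entry nor at Days 1, 2 and 7, and is smaller for neck symptoms.

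The size is unknown. A reader might be tempted to put a number on the subjects miscounted, but that would need both the share with such pain at entry and the share in whom it persists, and the documents give neither. Pain still reported at 1 month is also not the same as pain unchanged since entry.

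The conclusion assumes that the Data Sheet adds no baseline neck or back item. The effect is on the interpretation of one secondary endpoint in a descriptive pilot. No primary endpoint, error rate or sample size is touched, and the severity is minor. It still merits action, because a pre-block state cannot be recorded prospectively once the block has been given.

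**What to change.** First check the Data Sheet. If it already has baseline neck and back items, state this in section 7.2.1. If it does not:

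- Record presence and 0-10 severity of neck pain and of back pain together with the pre-block pain score.
- Repeat both items at Days 1, 2 and 7 and at 1 month.
- Use one 1-month item list (headache, neck pain, back pain, other) in sections 7.2.1, 7.2.3 and 7.3.
- In section 8.3, report 1-month neck and back pain as new, worse, unchanged or improved from pre-block, separately from side effects of the block.
- Show subjects who had an epidural blood patch separately.

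The cost is two extra questions before the block and at contacts already planned, with small edits to the form and the text. No visit or procedure is added.

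### Satisfaction is scheduled only at about 1 month and asks about overall management of the headache, so the rating cannot be attributed to the SP block

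*Combined protocol and SAP*

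**What the plan says.** Section 1.3 lists as secondary endpoint 2 "To measure patient satisfaction", with no scale, time point or object of the rating. Section 7.3 supplies the time and the object: "The participants will be contacted by phone about 1 month after the procedure", and at that call "They will also be asked if they are satisfied with their management of PDPH". Sections 7.2.1 and 7.2.3 agree; the 1-month call is made "to ask for any residual headache or other symptoms and their satisfaction with the management".

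For Days 1, 2 and 7, section 7.2.2 lists the questionnaire content as "pain relief, residual pain (intensity and location), side effects, nasal bleeding (See Data Sheet in supporting materials". Section 7.3 adds the original complaints and any new symptoms. Satisfaction is in neither list.

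Section 7.2.1 offers a blood patch or conservative care if the block fails or the headache comes back, and section 7.3 keeps these subjects in the call schedule. Sections 8.3 and 10.7 list the outcomes to be described, and satisfaction is not among them. Section 7.1 gives the design as open-label with one arm.

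**The concern.** The only objective in section 1.1 is how well the block relieves the headache. The two other secondary endpoints in section 1.3 name the block explicitly. A satisfaction percentage reported beside them is easily read as satisfaction with the block.

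The question as scheduled covers everything that happened to the subject over about a month. A subject whose block failed and whose blood patch worked can truthfully say that the management was satisfactory. So can a subject whose block failed and who recovered with rest and fluids. These answers count the same as that of a subject relieved by the block. Section 8.2 intends the pilot data to help plan a larger study, so it matters what the figure describes.

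**Working it through.** There is no sample-size or power figure to reproduce: the 30 subjects are a convenience sample (section 8.2), and the point does not depend on that number. The check is a timeline, followed by a list of what the rating contains.

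**Inputs**
- Puncture to enrolment: 0 to 7 days (section 3.1).
- Headache definition: bouts that "develop within 7 days after a lumbar puncture and disappears within 14 days" (section 2.1, quoted there from an outside classification).
- Call at about 1 month after the block, taken as 30 days (assumption).
- Blood patch effective in about 90% (section 2.1).

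**When the satisfaction call falls**
- Day of call after puncture = day of block + 30. Block on day 0: 0 + 30 = 30. Block on day 7: 7 + 30 = 37.
- If the 14 days run from puncture, the gap between that limit and the call is 30 − 14 = 16 to 37 − 14 = 23 days.
- If they run from onset, onset cannot be later than the block, because the subject must already have symptoms to enrol. The latest limit is then 14 days after the block, and the gap is at least 30 − 14 = 16 days.
- If 1 month means 28 or 31 days, the minimum gap is 28 − 14 = 14 or 31 − 14 = 17 days.

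**When the earlier contacts fall**
- Day 1 contact: day 0 + 1 = 1 to 7 + 1 = 8 after puncture.
- Day 7 contact: day 0 + 7 = 7 to 7 + 7 = 14 after puncture.
- If the limit runs from puncture, both contacts fall no later than day 14. Day 1 is well ahead of it.

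**What the 1-month rating contains**
- Block worked, no recurrence: the block plus the advice in section 7.2.1 on fluids, caffeine and rest for three days, plus natural resolution.
- Block failed or headache recurred, blood patch chosen: the block plus a procedure that the protocol describes as about 90% effective.
- Block failed or headache recurred, conservative care chosen: the block plus rest, pain medication and fluids, which section 5.1.1.2 presents as part of current standard treatment, plus natural resolution.

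All three groups answer the same question. No planned analysis separates them, and no control arm shows what the rating would be without the block.

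**The case against.** The strongest reply is that satisfaction is a retrospective judgement. A subject without a headache at 1 month can still remember that the block failed and that days in bed followed. In never-rescued subjects whose block worked, the care being rated is essentially the block plus simple advice. This stands: the rating is delayed and confounded, not empty.

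A reader might nevertheless infer that the 1-month rating cannot reflect the block at all, even without rescue, or that it must sit near its ceiling. The documents support neither. One could calculate the share of subjects free of headache at the call under an assumed rate of natural resolution. That would describe headache status, not satisfaction, and nothing in the documents links the two. It would also need a resolution rate that the documents do not give, and ignoring rescue would contradict section 7.2.1. Section 2.1 says only that the headache usually subsides within 1-2 weeks and warns of lasting neck and back pain if it is untreated. Section 3.1 admits subjects on suggestive symptoms, without the 14-day criterion.

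It can also be said that endpoint 2 does not name the block, so overall satisfaction may be exactly what was intended. That is a fair reading. If so, the question fits the endpoint, but the result needs that label and says little about the study's one objective.

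Finally, section 7.2 refers to a Data Sheet that was not available for review. It may hold a scale or further items. The point therefore rests on the protocol's own descriptions, which consistently place satisfaction only at 1 month.

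**Conclusion.** As described in the protocol, satisfaction is rated once, at about 1 month, for the whole course of care. On the definition quoted in section 2.1, the headache would usually have resolved at least 16 days before the call (14 to 17 if 1 month means 28 to 31 days). Rescued subjects answer the same question, and there is no comparator. The rating therefore cannot be attributed to the block, though it remains a usable measure of overall care.

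How far rescue and natural resolution shift the satisfaction percentage cannot be calculated from the documents, which give neither a rescue rate nor a distribution of ratings. The primary endpoints and the pain-relief questions on Days 1, 2 and 7 are unaffected. This is an inexpensive improvement to a secondary endpoint, not a threat to the study. It assumes that the Data Sheet holds no earlier or block-specific satisfaction item.

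**What to change.** - Add one item to the existing Day 1 and Day 7 contacts: satisfaction with the SP block itself, on a fixed scale. Ask subjects who have already had rescue specifically about the block.
- Name one of the two ratings in advance as the block-satisfaction endpoint in section 1.3, for example Day 1, and report the other descriptively. Day 1 leaves less time for rescue and natural resolution; Day 7 captures more recurrences.
- Keep the 1-month question, label it overall satisfaction with care, and report it separately for rescued and never-rescued subjects.
- Add both measures to the list of descriptive outcomes in section 8.3.

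The cost is one question at two contacts already scheduled and a line in each of sections 1.3 and 8.3. An early rating may miss later disappointment from recurrence, which the Day 7 rating partly covers. Splitting the 1-month result also widens its intervals. For illustration, with 80% satisfied, the exact 95% interval is 61% to 92% for 24 of 30; if half the subjects were never rescued (assumption), it is 52% to 96% for 12 of 15. The change does not create a comparator, so even the early rating stays descriptive, but it concerns the block and is given much closer to it.

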7.4 Test Article(s) (Study Drug(s) and/or Study Device(s))

7.4.1 Description

2% Lidocaine jelly (Glydo) is an approved local anesthetic agent permitted to be used over mucosal surfaces.

7.4.2 Treatment Regimen

A maximum of 6 mL of 2% lidocaine will be used which is within the therapeutic dose.

7.4.3 Method for Assigning Subject to Treatment Groups

It is an open label single arm study.

7.4.4 Subject Compliance Monitoring

The patient needs to comply with the telephonic conversation

